3.12. Clinical Safety Laboratory Tests

Blood and urine samples will be collected for testing the following clinical laboratory parameters at Screening, Day 90, and the Day 180 Visit.

Table 11: Clinical Safety Laboratory Parameters

Hematology	Biochemistry	Urinalysis
Hemoglobin	Glucose	Glucose
Hematocrit	Sodium	Protein
Red blood cell	Potassium	Specific gravity
White blood cell (WBC)	Calcium	pH
Platelets	Chloride	Ketones

Table 11: Clinical Safety Laboratory Parameters (Continued)

Hematology	Biochemistry	Urinalysis
WBC Differential	Carbon dioxide (CO ₂)	Bilirubin
	Inorganic phosphate	Urobilinogen
	Blood urea nitrogen (BUN)	Nitrite
	Creatinine	Blood ^a
	Creatinine clearance (estimated)	Leukocytes ^a
	Aspartate transaminase (AST)	
	Alanine transaminase (ALT)	
	Gamma-glutamyl transferase (GGT)	
	Total bilirubin (TBL) (direct bilirubin reflex if elevated)	
	Albumin	
	Alkaline phosphatase (ALP)	
	Uric acid	

^a Microscopic examination will be performed if blood or leukocytes are detected by dipstick.

Any new clinically significant laboratory abnormality observed, will be considered as an AE or SAE as appropriate.

3.13. Pregnancy Test

Female subjects of child-bearing potential must have a negative pregnancy test at Screening and Day 1 to be enrolled in the study. Female subjects of child bearing potential will undergo a serum pregnancy test at the Screening Visit and urine pregnancy tests at Day 1, Day 22, Day 43, Day 90, and Day 180/ET Visits. Any female subject that becomes pregnant during the study will be immediately withdrawn from treatment and will have the pregnancy reported.

3.14. Body Dysmorphic Disorder Questionnaire

The Body Dysmorphic Disorder Questionnaire (BDDQ) is validated, 4-question self-administered assessment tool used to screen for body dysmorphic disorder.^[5]

The questionnaire will ask the subject about concerns with physical appearance. The responses will be binary in nature. The BDDQ will be administered to all subjects at the Day 180 Visit.

BDDQ assessment should be completed independently of, and prior to, any investigator cellulite assessments (CR-PCSS, I-GAIS).

Table 12: Body Dysmorphic Disorder Questionnaire

Question No.	Question
1	Are you worried about how you look? (Yes/No) 
 • If yes: Do you think about your appearance problems a lot and wish you could think about them less? (Yes/No) 
 – If yes: List the body areas you don't like
2	Is your main concern with how you look that you aren't thin enough or that you might get too fat? (Yes/No)
3	How has this problem with how you look affected your life? 
 • Has it often upset you a lot? (Yes/No) • Has it often gotten in the way of doing things with friends, dating, your relationships with people, or your social activities? (Yes/No) 
 – If yes: Describe how.

Table 12: Body Dysmorphic Disorder Questionnaire (Continued)

Question No.	Question
	
 • Has it caused you any problems with school, work, or other activities? (Yes/No) 
 – If yes: What are they? • Are there things you avoid because of how you look? (Yes/No) 
 – If yes: What are they?
4	On an average day, how much time do you usually spend thinking about how you look? 
 • Less than 1 hour a day. • 1-3 hours a day. • More than 3 hours a day.

3.15. Body Height, Body Weight, and BMI

Height and body weight measurements will be taken at screening. Body weight will also be measured at the Day 1, 22, 43, 90, and 180 Visits. BMI will be calculated using the height at screening and weight at respective visits. Refer to [Table 18](#) for BMI derivation.

3.16. Vital Signs

Vital signs measurements include systolic and diastolic blood pressure, respiratory rate, pulse rate, and body temperature.

Vital signs measurements will be taken at the Screening, Day 1, 22, 43, 90, and 180 Visits. On treatment visits (Days 1, 22, and 43), vital signs will be assessed at 4 hours prior to, and at 15 and 30 minutes after study drug administration.

The investigator will review all vital sign values for clinical significance. Any clinically significant abnormality in vital sign observed will be considered as an AE or SAE as appropriate.

3.17. 12-Lead Electrocardiogram

A 12-Lead ECG will be recorded during screening while the subject is in a supine position for at least 5 minutes before the recording is conducted.

ECGs will be assessed by the investigator and graded as:

- Normal
- Abnormal, not clinically significant.
- Abnormal, clinically significant.

Any clinically significant abnormality in ECG observed will be considered as an AE or SAE as appropriate.

3.18. Physical Examination

A complete physical examination (by body system) will be performed at the Screening, Day 90 and 180/ET Visits. This evaluation will include an examination of head, eyes, ears, nose, throat, neck (including thyroid), cardiovascular system (including assessment of heart, peripheral pulses, presence or absence of edema), lungs, abdomen (including liver and spleen, bowel sounds), lymph nodes, musculoskeletal system (including spine, joints, muscles) neurological system (including cranial nerves, reflexes, sensation, strength), skin (excluding

cellulite), extremities, and other conditions of note. Physical examination findings will be recorded as normal, abnormal or not done as not standard of care.

Any clinically significant abnormality in physical examination observed will be considered as an AE or SAE as appropriate.

The subject's skin type and propensity for tanning will be assessed at screening using the Fitzpatrick scale (6-level scale [levels I-VI]) shown below:

Table 13: Fitzpatrick Scale

I	Pale white skin, blue/hazey eyes, blond/red hair	Always burns, does not tan
II	Fair skin, blue eyes	Burns easily, tans poorly
III	Darker white skin	Tans after initial burn
IV	Light brown skin	Burns minimally, tans easily
V	Brown skin	Rarely burns, tans darkly easily
VI	Dark brown or black skin	Never burns, always tans darkly

3.19. Immunogenicity

Immunogenicity variables include anti-AUX-I /anti-AUX-II binding antibodies (ie, anti-drug antibodies) and neutralizing antibody results. Serum samples will be collected at Day 1 (prior to study treatment administration) and at the Day 90 and Day 180 Visits for the determination of serum anti-AUX-I and anti-AUX-II antibody levels and neutralizing antibodies to AUX-I and AUX-II.

All safety assessments described above will be evaluated as per Schedule of Activities. Virtual visits are allowed to assess safety during any COVID-19 interruption.

4. STUDY PARAMETERS

4.1. Subject Disposition

Subjects will be considered to have completed the study if they complete the Day 180 Visit. Subjects who discontinue from study treatment or withdraw from the study for any reason after the Day 1 dosing will be encouraged to complete the remaining study visits and evaluations and provide any additional follow-up information as required by the study, unless the subject specifically indicates that they will not participate in any further evaluations.

If a subject withdraws from the study, all Early Termination procedures should be conducted as detailed in the Schedule of Activities. The reason and date for early withdrawal will be recorded in the eCRF for subjects who do not complete the study. If, however, a subject withdraws consent, no additional procedures are required except the collection of AE information. This information should be recorded in the source documentation and the eCRF. The reason for screen failure will also be recorded in eCRF for subjects who sign consent but do not receive any dose of study treatment.

4.2. Demographics and Baseline Characteristics

Demographics and baseline characteristics include the following parameters:

- Age.
- Height (at Screening).
- Body weight (at Screening).

- BMI in kg/m² (at Screening).
- Gender.
- Race.
- Ethnicity.
- Time since last menstrual period.
- CR-PCSS cellulite severity ratings for thigh and buttock at Screening.
- Hexsel CSS Section D (laxity, flaccidity or sagging of skin) scores at Screening.
- Skin category based on Fitzpatrick scale assessment.
- Report of tobacco and alcohol use
 - Alcohol use (Never, Current, and Former).
 - Tobacco use (Never, Current, and Former).

4.3. Protocol Deviations

Protocol deviations will be identified and documented prior to database lock. Protocol deviations will be derived from the eCRF data, electronic vendor data, and from the clinical monitoring reports. All deviations from these sources will be reconciled and duplicate deviations will be removed. When a deviation is both found in the database and in clinical monitoring reports, in most cases the text of the deviation from the database will be retained. The exception to this rule will occur if the deviation from the monitoring report provides important information not found in the database.

Possible protocol deviations include, but are not restricted to the following types:

- Ineligible subject/study entry criteria not satisfied.
- Informed consent not completed correctly.
- Non-compliance with study treatment.
- Prohibited medications/procedure.
- Visit/procedure missing or out of window.

The Endo study team will approve all final protocol deviation assignments and classify them as either major or minor during ongoing protocol deviation review meetings with the final meeting held prior to the database lock.

4.4. Prior/Concomitant Medications

All medications will be coded using World Health Organization (WHO) Drug Dictionary, by active ingredient and WHO anatomical therapeutic chemical (ATC) classification of ingredients.

A prior medication is defined as any medication taken within the 90 days prior to the Screening Visit.

A concomitant medication is any medication taken between the Screening Visit and the Day 180 Visit or 28 days after the last study treatment for those who terminate early or the medication is reported as ongoing.

4.5. Prior EFP Treatment

Prior EFP treatment will be obtained from the prior/concomitant medication and/or prior/concomitant procedure pages of the eCRF. If on either of these pages a medication or procedure is reported with the indication ‘EFP/Cellulite’ prior to the Screening Visit, then the medication or procedure will be considered a prior EFP treatment.

All EFP treatment medications will be classified as EFP Drug. All EFP treatment procedures will be classified into one of the following groups:

- Liposuction.
- Surgery (including subcision and/or powered subcision).
- Laser.
- Massage.
- Radiofrequency.
- Mesotherapy.
- Cream.
- Other.

The classification will be reviewed and approved by the study medical monitor. Any EFP treatment used after the Day 1 visit will be noted and reported as a protocol deviation.

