6.7.1. Prohibited Medications and Procedures

The following medications are prohibited for subjects during the study:

- Anticoagulants (warfarin, heparin, direct thrombin inhibitors, Factor X inhibitors) and antiplatelet agents (aspirin > 150 mg/day and P2Y12 inhibitors, such as clopidogrel), which can cause additional bruising. However the use of aspirin at a dose level of ≤ 150 mg per day will be permitted during study.

The following procedures/treatments are not allowed in the selected treatment region (both buttocks or both thighs) during the course of the study (from the Screening Visit through the Day 180 End of Study/Early Termination Visit):

- Liposuction.
- Any injectable treatment (eg, KYBELLA) or any similar treatment that could destroy fat cells and/or remove fat deposits.
- Injections (eg, mesotherapy); radiofrequency device treatments; laser treatment; buttock implant treatment; cryolipolysis; or surgery (including subcision and/or powered subcision).
- Any investigational treatment for EFP (other than CCH as prescribed in this study).
- Endermologie or similar treatments.
- Massage therapy.
- Creams (eg, Celluvera, TriLastin) and/or home therapies to prevent or mitigate EFP.

If any prohibited medication or procedure is used during the study, all pertinent information will be recorded. The designated study medical monitor must be informed immediately so the sponsor may determine whether to continue the subject in the study.

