4.6. Efficacy Parameters

4.6.1. I-GAIS

4.6.1.1. I-GAIS Rating

The I-GAIS rating is directly obtained from the investigator’s assessments at an evaluation visit (Day 22, Day 43, Day 90, or Day 180).

In addition, the last observation carried forward (LOCF) will be used to impute any missing data at Day 90 Visit for the primary analysis.

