4.6.1.2. One-Level I-GAIS Responder for a Treatment Area

One-level I-GAIS Responder for a treatment area is defined as any subject with an improved (+1, +2 or +3) score on the I-GAIS at an evaluation visit for that treatment area.

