4.6.1.3. One-Level I-GAIS Responder for Either Buttock or Either Thigh

One-level I-GAIS Responder for either buttock is defined as any buttock-treated subject with an improved (+1, +2 or +3) score on the I-GAIS for at least one buttock at an evaluation visit.

One-level I-GAIS Responder for either thigh is defined as any thigh-treated subject with an improved (+1, +2 or +3) score on I-GAIS for at least one thigh at an evaluation visit.

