5. ANALYSIS POPULATIONS

The study will use the following analysis populations for data summaries.

Table 17: Analysis Populations

Population	Definition	Displays
Safety Population	The Safety Population will include all subjects who receive at least 1 injection of study medication.	All demographic and baseline characteristics as well as safety parameters will be summarized based on this population.
Evaluable Population	The Evaluable Population will include all subjects who receive at least 1 injection of study medication and have at least 1 I-GAIS evaluation.	All efficacy analysis will be based on this population.

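### I-GAIS response is defined by the rating alone, so a +1 recorded after a barred cellulite treatment counts as a response to CCH

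*SAP*

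**What the plan says.** Protocol 6.7.1 bars a list of procedures in the treated region from screening to Day 180. It includes liposuction, injections, radiofrequency, laser, cryolipolysis, surgery with subcision, massage and creams. If one is used, it is recorded and "The designated study medical monitor must be informed immediately so the sponsor may determine whether to continue the subject in the study".

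On the analysis side:

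- SAP 4.5: "Any EFP treatment used after the Day 1 visit will be noted and reported as a protocol deviation". SAP 4.3 and 7.2 classify, summarise and list deviations. SAP 7.6 adds a listing of medications and procedures for EFP/cellulite.
- SAP 4.6.1.1: "The I-GAIS rating is directly obtained from" the investigator's assessment at the visit.
- SAP 4.6.1.2, for one side: a responder "is defined as any subject with an improved (+1, +2 or +3) score on the I-GAIS at an evaluation visit for that treatment area".
- SAP 4.6.1.3, the subject-level rule used for the primary endpoint, has a buttock responder ("defined as any buttock-treated subject with an improved (+1, +2 or +3) score on the I-GAIS for at least one buttock at an evaluation visit") and a thigh responder ("any thigh-treated subject with an improved (+1, +2 or +3) score on I-GAIS for at least one thigh at an evaluation visit").
- SAP 5: the Evaluable Population is "all subjects who receive at least 1 injection of study medication and have at least 1 I-GAIS evaluation". It is the only efficacy set, as Table 17 states: "All efficacy analysis will be based on this population".
- SAP 6.3: a missing Day 90 I-GAIS takes the last non-missing rating.
- SAP 6.1: a subject removed from an analysis is footnoted with the reason, but no criterion for removal is given.

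**The concern.** The primary objective is the efficacy of CCH. I-GAIS compares a later image with the Day 1 image, so it cannot tell a change due to CCH from a change due to another cellulite treatment given in between. The plan records that treatment but does not let it affect the endpoint. In the readable text there is no per-protocol set, no recoding rule and no sensitivity analysis for these subjects.

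A randomised comparison would offer some protection if both arms behaved alike. Here each cohort's proportion is read on its own. The same proportion in the first 40 or so thigh subjects also decides whether the sample size is revisited (SAP 6.4). If the question is settled only after the ratings and deviations are known, the choice is made with open-label results in view.

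**Working it through.** **1. Does any rule stop the rating from counting?** Take a thigh subject dosed on Day 1 who has laser on the thighs before Day 90 and is rated +1 at Day 90.

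- She has an injection and an I-GAIS rating, so she is in the Evaluable Population.
- Her score is +1 on at least one thigh, so she is a responder under SAP 4.6.1.3.
- Her laser treatment appears in the deviation summary and the listings, and nowhere else.
- If the sponsor withdraws her before Day 90, Protocol 7.2 calls for Early Termination procedures, which include I-GAIS in the Schedule of Activities. SAP 6.3 carries forward the last non-missing rating with no cut-off at the date of the laser treatment, so the carried rating can be one made after it.

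The gap therefore exists for both Day 90 and Day 90 (LOCF).

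**2. The plan's own precision figure.** Inputs from Protocol 9.1 and SAP 3.6.1: 70 buttock and 80 thigh subjects, true rates 70% and 60%, floors 60% and 50%, a 95% chance, 10% dropout. Evaluable n: 70 × 0.9 = 63 and 80 × 0.9 = 72.

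P(estimate ≥ floor) ≈ Φ[(p − floor)/√(p(1 − p)/n)]

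- Buttock: 0.10/√(0.7 × 0.3/63) = 0.10/0.0577 = 1.73, giving 95.8%.
- Thigh: 0.10/√(0.6 × 0.4/72) = 0.10/0.0577 = 1.73, giving 95.8%.

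The exact binomial gives 96.3% and 96.7%. The stated 95% is reproduced, so 63 and 72 are reasonable denominators.

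**3. Effect of recoding.** Let k be the number of counted responders who had a barred treatment. The documents give no value, so 0 to 7 per cohort is an assumption. The recoded rate is (x − k)/n, with x = 43 of 72 (thigh) and 44 of 63 (buttock), the nearest whole numbers to the planned rates. Intervals are Wilson 95%, as in SAP 7.7.1.1.

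| k | Thigh, n = 72 | Buttock, n = 63 |
|---|---|---|
| 0 | 43/72 = 59.7% (48.2 to 70.3) | 44/63 = 69.8% (57.6 to 79.8) |
| 1 | 42/72 = 58.3% | 43/63 = 68.3% |
| 3 | 40/72 = 55.6% (44.1 to 66.5) | 41/63 = 65.1% (52.8 to 75.7) |
| 7 | 36/72 = 50.0% (38.8 to 61.3) | 37/63 = 58.7% (46.4 to 70.0) |

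Per subject: 1/72 = 1.4 points and 1/63 = 1.6 points. If LOCF fills every missing rating, the denominators approach 80 and 70, and the steps become 1.25 and 1.4 points.

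**4. Recoding effect against bias.** The table shows what recoding does. It equals the inflation only if none of the k subjects would have responded to CCH alone. Suppose instead that use is unrelated to response and the other treatment always yields +1. Then the expected inflation per user is (1 − 0.6) × 1.4 = 0.6 points for thighs and (1 − 0.7) × 1.6 = 0.5 points for buttocks. If users are mainly CCH non-responders, it moves towards the full 1.4 and 1.6.

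**5. Interim.** SAP 6.4 allows the thigh sample size to be adjusted if the proportion is below 50% in about 40 subjects. 20/40 = 50.0% does not meet the condition; with one subject recoded, 19/40 = 47.5% does.

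**The case against.** The study describes itself as real world and exploratory, and its primary analysis is a proportion with an interval. Counting ratings as observed, whatever else the subject used, is a recognised strategy. Conduct safeguards also exist. Women intending such treatment are excluded (Protocol 5.2, criterion 8), use goes to the medical monitor at once, and a protocol violation can lead to withdrawal. Deviations, EFP treatments and ratings are all listed, so a reader could find the affected subjects.

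Much of this stands as a limit on size. It does not close the gap, because the safeguards act on conduct and display, and the counting rule is unchanged. The plan nowhere says that as-rated counting is a deliberate choice, and it sits awkwardly with an objective worded as CCH efficacy and a protocol that forbids these treatments.

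It is also fair that non-responder coding is conservative: a subject rated +2 at Day 43 who then has one massage would lose her response. This is why the as-rated result should be kept beside it.

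A reader might infer more than the documents support:

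- *That the protocol bars these treatments because they alter the rated appearance.* Section 6.7.1 gives no general reason. It mentions bruising for anticoagulants and antiplatelets, and fat destruction or removal for one item.
- *That every such rating inflates the rate.* A subject already improved by CCH who later uses a cream changes nothing, and Protocol 2.2 describes the evidence for many existing therapies as weak.
- *That Day 180 is worst affected because of COVID-19 delay.* The rescheduling rules keep Day 180 at 180 (+14) days for two of the three interrupted groups. The clearer lengthening is before Day 90: with the delayed dosing visit at its limit, Day 90 falls at least 100 + 21 + 28 = 149 days after first dose for one-dose subjects, and 121 + 28 = 149 for two-dose subjects.

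**Conclusion.** The gap is real and should be closed before database lock. As written, a rating of +1 or better after a barred cellulite treatment is a CCH response, at the visit and possibly through LOCF. The expected direction is upward.

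The size cannot be stated. It depends on how many subjects used such treatment, which the documents do not give, and on how many of them would have responded to CCH anyway. The firm figures are the steps per recoded subject: 1.4 points for thighs and 1.6 for buttocks after 10% dropout, each an upper bound on the inflation. A shift of several points needs several such subjects, and presenting it as the bias would go beyond the documents. With few users the effect is small beside a thigh interval of about 48% to 70%. The interim is where a single subject could change a decision.

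**What to change.** In SAP 4.6.1, state that a subject is a non-responder at every later visit, and at Day 90 (LOCF), if after the first dose she has either:

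- a medication or procedure other than study CCH recorded with the indication EFP/Cellulite, which is the flag SAP 4.5 already uses; or
- a Protocol 6.7.1 procedure documented on the treated region.

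The indication flag comes first because the fields listed in Protocol 6.7 and SAP 3.10 do not include anatomical site, so a rule resting on location alone might not be derivable.

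Report the as-rated proportion as a sensitivity analysis, and footnote the number reclassified by cohort and visit. If the interim is still to be run, apply the same rule there.

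For CR-PCSS and Body-Q, keep the observed summaries and add a sensitivity summary without the later values. Setting those values to missing in the main summary could raise the mean improvement, if the subjects who sought other treatment were the less satisfied ones.

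The cost is a few sentences, one derived flag from data already collected and one extra table. The responder rate may be slightly less favourable, and it is conservative, since some recoded subjects may be true CCH responders.

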4.6. Efficacy Parameters

4.6.1. I-GAIS

4.6.1.1. I-GAIS Rating

The I-GAIS rating is directly obtained from the investigator’s assessments at an evaluation visit (Day 22, Day 43, Day 90, or Day 180).

In addition, the last observation carried forward (LOCF) will be used to impute any missing data at Day 90 Visit for the primary analysis.

4.6.1.2. One-Level I-GAIS Responder for a Treatment Area

One-level I-GAIS Responder for a treatment area is defined as any subject with an improved (+1, +2 or +3) score on the I-GAIS at an evaluation visit for that treatment area.

